9.13. Physical Examinations

A brief physical examination will be performed at each visit, including, at a minimum, assessments of:

- **Skin Assessment:** As part of the assessment, the skin will be examined for any anomalies, such as lesions, rashes, or discolorations.
- **Assessment of the Cardiovascular System:** This involves evaluating the heart and blood vessels as well as the cardiovascular system. The participant's pulse, blood pressure, and heart sounds will be evaluated.
- **Respiratory System Assessment:** The examination will include an evaluation of the respiratory system, focusing on lung function assessing the participant's breathing rate and depth, looking for signs of respiratory distress, or listening for breath sounds that could indicate respiratory issues. The state of the lungs will be assessed, usually using auscultation.

- Abdominal Assessment (Liver and Spleen): The abdominal assessment will involve palpation (gentle pressing) of the abdomen to check for any tenderness, masses, or organ enlargement, specifically focusing on the liver and spleen. This helps to detect any hepatosplenic abnormalities or discomfort in the abdominal region.
- Investigators should pay special attention to clinical signs related to previous serious illnesses.

9.13.1. Vital Signs

- Pulse rate, respiratory rate, and blood pressure will be recorded (before blood collection for laboratory tests).
- Blood pressure and pulse measurements will be assessed in a supine position.
- Blood pressure and pulse measurements should be preceded by at least 5 minutes of rest for the participant in a quiet setting without distractions (eg, television, cell phones).

9.14. Electrocardiograms

- 12-lead ECG(s) will be obtained as outlined in the SoA (see Section 1.3) using an ECG machine that automatically calculates the heart rate and measures PR, QRS, QT, and QTc intervals will be evaluated. Clinical Safety Laboratory Tests

9.15. Clinical Safety Laboratory Tests

- See Appendix 2 for the list of clinical laboratory tests to be performed and the SoA (Section 1.3) for the timing and frequency.
- The investigator must review the laboratory results, document this review, and record any clinically significant changes occurring during the study as an AE. The laboratory results must be retained with source documents.
- Abnormal laboratory findings associated with the underlying disease are not considered clinically significant unless judged by the investigator to be more severe than expected for the participant's condition.
- All laboratory tests with values considered clinically significantly abnormal during participation in the study or within [insert timeframe] after the last dose of study intervention should be repeated until the values return to normal or baseline or are no longer considered clinically significant by the investigator or medical monitor.
 - If clinically significant values do not return to normal/baseline within a period of time judged reasonable by the investigator, the etiology should be identified, and the sponsor notified.
 - All protocol-required laboratory tests, as defined in Appendix 2, must be conducted in accordance with the laboratory manual and the SoA (Section 1.3).
 - If laboratory values from non-protocol-specified laboratory tests performed at the institution's local laboratory require a change in participant management or are considered clinically significant by the investigator (eg, SAE or AE or dose modification), then the results must be recorded.

9.16. Suicidal Ideation and Behavior Risk Monitoring

Participants will be monitored appropriately and observed for suicidal ideation and unusual behavior. Items from the Columbia-Suicide Severity Rating Scale (C-SSRS) will be used as a guide. If signs of suicidal behavior are observed, a risk assessment will be conducted. When informed consent or assent has been given, the informant should be alerted about the need to monitor participants for the emergence of unusual changes in behavior, as well as the emergence of suicidal ideation and behavior and to report such symptoms immediately to the study investigator.

9.17. Adverse Events (AEs) Serious Adverse Events (SAEs), and Other Safety Reporting

The definitions of adverse events (AEs) and serious adverse events (SAEs) can be found in Appendix 3.

The investigator and any qualified designees are responsible for detecting, documenting, and recording events that meet the definition of an AE or SAE and remain responsible for following up all AEs considered related to the study intervention or study procedures, or that caused the participant to discontinue the study intervention (see Section 7). This includes events reported by the participant (or, when appropriate, by a caregiver, surrogate, or the participant's legally authorized representative). Adverse events will be discussed with the local study doctor, and as needed discussed with the medical monitor. Based on the severity considering the safety of the participants, a decision will be made regarding dose reduction, pausing the study drug, or withdrawing the participant from the study.

The method of recording, evaluating, and assessing causality of AEs and SAEs and the procedures for completing and transmitting SAE reports are provided in Appendix 3.

9.17.1. Time Period and Frequency for Collecting AE and SAE Information

All SAEs will be collected from the start of treatment until the last follow-up visit at the timepoints specified in the SoA (Section 1.3).

All AEs will be collected from the start of treatment until the last follow-up visit according to the timepoints specified in the SoA (Section 1.3).

Medical occurrences that begin before the start of study intervention but after obtaining informed consent will be recorded as medical history/current medical conditions, not as AEs.

All SAEs will be recorded and reported to the sponsor immediately and under no circumstance should this exceed 24 hours, as indicated in Appendix 4. The investigator will submit any updated SAE data to the sponsor within 24 hours of it being available.

Investigators are not obligated to actively seek information on AEs or SAEs after conclusion of the study participation. However, if the investigator learns of any SAE, including a death, at any time after a participant has been discharged from the study, and the investigator considers the event to be reasonably related to the study intervention or study participation, the investigator must promptly notify the sponsor.

9.17.2. Method of Detecting AEs and SAEs

Care will be taken not to introduce bias when detecting AEs and/or SAEs. Open-ended and nonleading verbal questioning of the participant is the preferred method to inquire about AE occurrences. All adverse events (AE) will be collected from start of treatment until resolution or

until the investigator assesses AE as “chronic” or “stable”. Each AE is to be classified by the investigator as “serious” or “non-serious”. This classification of the gravity of the event determines the reporting procedures to be followed. The intensity of AE will be graded using the Common Terminology Criteria for Adverse Events (CTCAE) of the U.S. Department of Health and Human Services. If a serious AE (SAE) occurs, reporting will follow local and international regulations, as appropriate. All SAE will monitor for (1) a relationship between SAE and trial medication, (2) expectedness of SAE (derived from reference safety information of approved formulation of phenserine) (3) benefit/risk assessment for the clinical trial did change as a result of SAE, and (4) safety issues, which are sufficient to consider changes in the conduct of the clinical trial. Additionally, the investigator must make a causality assessment for all AEs. In case of a causal relationship with at least reasonable relationship between occurrence of AE and study medication, the AE will be determined as adverse reaction (AR). A case of a serious AR (SAR) that is unexpected with respect to reference safety information of the approved formulation of phenserine will be determined a Suspected Unexpected Serious Adverse Reaction (SUSAR) and requires expedited reporting according to the legal framework (competent authorities, ethic committees, clinical trial sites). Further details are provided in Appendix 3.

A summary of the nonclinical and clinical safety and pharmacokinetics data of phenserine is available in section 6 (page 29) of the Investigator’s Brochure. The section includes a description of serious adverse events and adverse events reported in other clinical trials with phenserine.

9.17.3. Follow-up of AEs and SAEs

After the initial AE/SAE report, the investigator is required to proactively follow each participant at subsequent visits/contacts. All SAEs will be followed until resolution, stabilization, the event is otherwise explained, or the participant is lost to follow-up (as defined in Section 7.3). Further information on follow-up procedures is provided in Appendix 3.

9.17.4. Regulatory Reporting Requirements for SAEs

- Prompt notification by the investigator to the sponsor of an SAE is essential so that legal obligations and ethical responsibilities towards the safety of participants and the safety of a study intervention under clinical investigation are met.
- The sponsor has a legal responsibility to notify both the local regulatory authority and other regulatory agencies about the safety of a study intervention under clinical investigation. The sponsor will comply with country-specific regulatory requirements relating to safety reporting to the regulatory authority, institutional review boards (IRBs)/independent ethics committees (IECs), and investigators.
- An investigator who receives an investigator safety report describing an SAE or other specific safety information (eg, summary or listing of SAEs) from the sponsor will review and then file it and will notify the IRB/IEC, if appropriate according to local requirements.
- Investigator safety reports must be prepared for suspected unexpected serious adverse reactions (SUSARs) according to local regulatory requirements and sponsor policy and forwarded to investigators as necessary.

9.17.5. Annual Safety Report (ASR) Responsibility

- In accordance with the Clinical Trial Regulation (CTR, EU 536/2014), Annex III, the sponsor is responsible for the preparation and submission of the Annual Safety Report (ASR) for this clinical trial. The ASR will summarize the safety data collected over the reporting period, including an analysis of adverse events, serious adverse events, and other safety findings.

9.17.6. Pregnancy

- Details of all pregnancies in female participants, will be collected after the start of the study intervention and until the study end.
- If a pregnancy is reported, the investigator will record pregnancy information on the appropriate form and submit it to the sponsor within 24 hours of learning of the pregnancy.
- While pregnancy itself is not considered to be an AE or SAE, any pregnancy complication or elective termination of a pregnancy for medical reasons will be reported as an AE or SAE.
- Abnormal pregnancy outcomes (eg, spontaneous abortion, fetal death, stillbirth, congenital anomalies, ectopic pregnancy) are considered SAEs and will be reported as such.
- The participant will be followed to determine the outcome of the pregnancy. The investigator will collect follow-up information on the participant and the neonate, and the information will be forwarded to the sponsor.
- Any poststudy pregnancy-related SAE considered reasonably related to the study intervention by the investigator will be reported to the sponsor as described in Section 8.3.3. While the investigator is not obligated to actively seek this information in former study participants, he or she may learn of an SAE through spontaneous reporting.
- Any female participant who becomes pregnant while participating in the study will discontinue study intervention and be withdrawn from the study.

9.17.7. Cardiovascular and Death Events

Cardiovascular events (eg coronary infarction) or cerebrovascular events (e.g. stroke) will be recorded. A QTc interval ≥ 460 milliseconds for males or ≥ 470 milliseconds for females will be considered abnormal during the ECG assessments.

9.18. Pharmacokinetics

- Plasma PK samples will be collected at W 2, 4, 6, and 8 visits for all IMP participants. Samples will be analyzed for phenserine to determine C_{max} and t_{1/2}. Available data will be analyzed by the DSMB to assess the safety of ongoing patients. PK samples will also be collected at the Week 8 visit, at peak dose, from all other patients (and at the final maintenance dose level for those who down-titrate due to tolerability) prior to taking the

morning dose, to establish steady-state concentration and stored for later analyses aimed at exploring the relationship between exposure and tolerability/efficacy outcomes.

- Instructions for the collection and handling of biological samples will be provided by the sponsor. The actual date and time (24-hour clock time) of each sample will be recorded. Samples will be used to evaluate the pharmacokinetics (PK) of phenserine. Each sample will be divided into aliquots as described in the SOP. These samples may also be used to evaluate safety or efficacy aspects related to concerns arising during or after the study.

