1.3. Schedule of Activities (SoA)**Table 1. Schedule of Activities**

	Screening (within 28 days before baseline)	Treatment Period					Safety Follow-up ¹ /EOS (within 28 days after last visit)
		Baseline	W2	W4	W6	W8	
Days \pm Visit window	-28 to 0	0	(14\pm 3)	(28\pm 3)	(42\pm 3)	(56\pm 3)	(56\pm 28)
Informed consent	X						
Demographics	X						
Medical history ²	X						
Concomitant medications	X	X	X	X	X	X	X
Vital signs	X	X	X	X	X	X	X
Physical Exam	X	X	X	X	X	X	X
Neurological Exam	X						X
ECG	X	X	X	X	X	X	X
MMSE	X						
MoCA		X				X	
CDR	X						
MRI ³	X						
Suicidal screening using C-SSRS, modified ⁴	X			X		X	X
Inclusion/Exclusion criteria	X	X					
Randomization		X					
Dispense of IMP ⁵		X	X	X	X		
Adverse events		X	X	X	X	X	
AchE sample collection		X	X	X	X	X	

Dose review (for escalation or de-escalation)			X	X	X		
Exosome Biomarker Collection		X	X	X	X	X	
Blood and CSF-based biomarkers ⁶	X					X ⁷	
PK sample collection			X	X	X	X	
Safety laboratory test ⁸	X		X	X	X	X	X
Urinalysis	X		X	X	X	X	X
FSH test ⁹	X						
Pregnancy test ¹⁰	X		X		X		
FLAME Cognitive battery		X				X	

¹ A safety follow-up visit will be conducted within ~4-weeks after the last study-drug dose for all participants who complete the study or who terminate early.

² Includes prior medication use.

³ Only if no MRI scan available within last 2 years.

⁴ The C-SSRS will only be conducted at the follow-up/EOS visit, if the patient experienced suicidal thoughts after the study treatment period.

⁵ Before any dose escalation. According to tolerability and laboratory tests, the dosage will be reassessed, and participants may need to return to the center for a reduced dose.

⁶ CSF samples will only be collected from patients who specifically consent to CSF sample collection and analysis. If CSF biomarker data are available then there is no need for a new CSF collection at screening

⁷ CSF collection at W8 is voluntary and requires an additional informed consent.

⁸ Renal and liver function will be taken every visit. Full Safety laboratory battery will be taken at screening and safety follow-up.

⁹ Women considered post-menopausal will have an FSH test to confirm their status during the screening period and prior to dosing.

¹⁰ Pregnancy testing is required for all women of childbearing potential within one day prior to receiving the first dose of study drug.

2. Introduction

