2.1. Study Rationale

This protocol aims to assess the safety and tolerability of phenserine compared to donepezil across various doses administered over a 8-week period in participants with early or mild AD. The study will also evaluate the pharmacodynamic and pharmacokinetic activity of the two drugs to determine dose-response relationships and identify an appropriate dose range for a subsequent Phase 2 study of phenserine.

This study seeks to evaluate the effects of an individualized maximum tolerated dose of phenserine with adequate AChE inhibition to establish an appropriate dose range for future efficacy trials.

The main objective is to test phenserine's disease modifying effect, and therefore we will include a comparator that controls for the known cholinesterase inhibition of phenserine, eg donepezil. This approach allows us to control for the symptomatic effects of cholinesterase inhibition, and to provide direct comparative data on safety and tolerability relative to a well-known AChE inhibitor.

The study duration is relatively short. This is justified by the following rationale: The cholinesterase inhibition effect occurs rapidly within a few hours after intake, and is sustained for about 6 hours. Thus the 4 week duration of the highest dose is sufficient to demonstrate this effect. The time of onset for the effect on cell death markers and other disease mechanisms is expected to start within 4 weeks but definitely within the full 8 weeks study period.

Donepezil, the most used cholinesterase inhibitor in AD with dementia, is included as comparison to control for the cholinesterase inhibition of phenserine, since the main rationale for the PATH1 trial is to explore whether phenserine has an additional disease-modifying effect, including effect on markers of cell-death.

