To evaluate compliance, the study will measure the extent to which participants take the study medication according to the protocol. Compliance will be assessed using the subject diary and the registration of returned capsules.

Exploratory Objectives:

To evaluate changes in specific biomarkers of Alzheimer's Disease (AD) in cerebrospinal fluid (CSF): A β 1-40, A β 1-42, Tau, and p-tau, and in blood plasma: p-tau217 and NfL.

To assess phenserine's potential short-term effects on specific cognitive tests using the FLAME Memory Composite and other cognitive sub-tests.

To evaluate changes in overall cognitive function using the Montreal Cognitive Assessment (MoCA):

Primary Endpoint:

Changes in exosome biomarkers of pre-programmed cell death, synaptic integrity and function, neuroinflammation, and AD-related protein trafficking in participants treated with phenserine versus those treated with donepezil. Although patients and site staff will be unblinded to the treatment modality administered, they will be blinded to the results of the biomarker evaluations until the study is completed.

Key Secondary Endpoints:

Safety and tolerability of phenserine compared to donepezil in participants with early or mild AD based on the frequencies of reported or observed adverse events (AEs) and serious adverse events (SAE), vital signs, clinical laboratory evaluations, ECGs, and modified CSSRS scores.

Other Secondary Endpoints:

Pharmacokinetic parameters will be assessed at steady state for determination of dose-response relationships for phenserine and donepezil.

Evaluate the proportion of participants in the phenserine arm who achieve the target AChE inhibition of approximately 45%, stratified by dose regime and assess the time required to reach the target AChE inhibition of ~45% and the duration participants maintain this inhibition during the treatment period. Blood samples will be analyzed for Acetylcholinesterase (AChE) activity using a modified Micro-Ellman method (22) normalized to recombinant AChE enzyme activity (refer to Appendix 10).

Compliance will be recorded, based on drug count and subject diary, including the proportion of participants complying with the treatment schedule. Compliance is defined as drug intake within 80-120% of the scheduled dosing.

Exploratory Endpoints:

Assess changes in Alzheimer's Disease (AD) biomarkers in cerebrospinal fluid (CSF): A β 1-40, A β 1-42, Tau, and p-tau, and in blood plasma: p-tau217 and NfL.

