10.3. Statistical Analyses

All primary, secondary and exploratory outcomes will be collected for all participants, except that PK analyses will be performed only for participants randomized to phenserine.

Trial management and data management will be conducted by the University Hospital Stavanger Clinical Trials Unit and the trial statistics will be led by [name], King's College London.

Standard safety data (including all AEs, TEAEs, SAEs, important clinical laboratory findings, and AE-related discontinuations) will be summarized for each treatment arm and dose level.

Exosome biomarker values will be natural log transformed to avoid skewness. To assess the effect of phenserine on a given biomarker, a linear mixed-effects model will be used, with treatment groups (phenserine vs donepezil), time, baseline biomarker, and plate to plate variability in exosome concentration (determined by NanoSight) as fixed effects and participant identification treated as a random effect.

To demonstrate that dropout rates are Missing at Random (MAR), we will calculate the correlation between dropout indicators (e.g., whether a participant drops out) and key covariates, including treatment group, baseline characteristics, and other relevant random effect categories. Based on prior observations (liraglutide trial for example), we expect that the likelihood of dropout will largely be explained by observed factors, especially drug treatment status. A logistic regression model will be used, with the dropout indicator as the dependent variable and treatment status, baseline covariates, and any other relevant factors as independent variables. If the model explains a significant portion of the dropout pattern, this would support the MAR assumption. Sensitivity analyses will also be conducted to assess the robustness of this finding under alternative missingness mechanisms.

For clinical secondary and exploratory outcomes, change from baseline will be calculated at the final study assessment (mean, n, standard deviation, standard error, minimum and maximum scores).

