4.4 Pharmacokinetic Population

All participants with sufficient PK samples to estimate at least one PK parameter.

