8.3 AChE Inhibition

- Proportion achieving $\geq 45\%$ inhibition
- Time to reach target inhibition
- Duration above target threshold

Summarized descriptively and graphically.

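### The PK schedule as written cannot give individual Cmax, Tmax or half-life, and uncaptured home-dose times could confound the exposure-response and AChE plots

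*Protocol*

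**What the plan says.** **Sampling.** Protocol 9.18: "Plasma PK samples will be collected at W 2, 4, 6, and 8 visits for all IMP participants". In Table 1 the row "PK sample collection" has a single mark at each of Weeks 2, 4, 6 and 8. The AChE row has single marks at baseline and the same four visits. Neither row gives a time relative to dose. The only timing is in 9.18, where a Week 8 sample from all other patients is taken before the morning dose. Collection instructions are left to the sponsor and to SOPs that are not part of the documents.

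**Parameters.** Protocol 9.18: "Samples will be analyzed for phenserine to determine C_{max} and t_{1/2". SAP 8.2 lists steady-state concentrations first, then Cmax, Tmax and AUC with a proviso about being derivable; it does not list half-life. It also plans exposure-response plots against AChE inhibition and key exosome markers. SAP 4.4 defines the PK population as "All participants with sufficient PK samples to estimate at least one PK parameter".

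**AChE endpoints.** Protocol Section 3 asks for the proportion reaching about 45% inhibition, the time to reach it, and how long it is maintained over the treatment period. SAP 8.3 includes "Duration above target threshold". SAP 4.5 types time to target as time-to-event and duration as continuous. Neither document gives a rule for the gaps between visits.

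**Clock times.** The time of each sample (9.18) and of each in-clinic dose (6.5) is recorded. Section 4.4 says the diary tracks dosing times, but the sample phenserine diary in Appendix 7 has only tick boxes for morning, afternoon and evening.

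**Which drug.** Section 3 and Table 2 state: "Pharmacokinetic parameters will be assessed at steady state for determination of dose-response relationships for phenserine and donepezil". Section 9.18 assays phenserine only, and Section 10.3 says "PK analyses will be performed only for participants randomized to phenserine". Table 3 lists both drugs as IMP.

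**The concern.** The protocol promises Cmax and half-life without qualification, from a schedule that appears to hold one untimed sample per visit. A half-life needs at least two timed points on the same decline. Cmax and Tmax need samples around the peak.

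The exposure-response use is the more practical worry. Section 3 says the PK and PD data are to inform Phase 2 dose selection. Dosing frequency changes from bd to tds between Weeks 4 and 6. If samples fall at different and unknown times after the last dose, a difference between dose levels could come partly from timing, or timing could hide a real difference. The same applies to AChE inhibition, of which Section 2.1 says "The cholinesterase inhibition effect occurs rapidly within a few hours after intake, and is sustained for about 6 hours".

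**Working it through.** The plan states no figure to reproduce. The check asks what the schedule can identify, then how large the timing effect could be.

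**Inputs.**
- Tmax 1.25–1.54 h and elimination half-life 6.53 h; fed Tmax 2.7 h; peak inhibition about 30% at 10 mg (all Protocol 2.3.1).
- Half-life of AChE inhibition 8.25 h (4.5).
- 5 mg bd in Weeks 1–2, 10 mg bd in Weeks 3–4, 10 mg tds in Weeks 5–8 (Tables 3 and 4).
- Doses are to be taken with food (2.3.1), so the fed row below is the closest to the trial.

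**Step 1: what can be identified.** At one draw per visit, each participant gives one concentration on 5 mg bd, one on 10 mg bd and two on 10 mg tds. Consecutive visits are 14 × 24 = 336 h apart, and 336 / 6.53 ≈ 51 half-lives. No two samples lie on the same decline, so there is no individual half-life. A pre-dose sample is a trough and gives neither Cmax nor Tmax. An AUC over the dosing interval also needs more than one point. Neither document plans serial sampling or a population PK model.

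**Step 2: size of the timing effect on concentration.** Assume a one-compartment oral model, linear kinetics, evenly spaced doses and steady state. With ke = ln 2 / 6.53, ka is solved from Tmax = ln(ka/ke)/(ka − ke), and

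C(t) ∝ D · ka/(ka − ke) · [e^(−ke·t)/(1 − e^(−ke·τ)) − e^(−ka·t)/(1 − e^(−ka·τ))].

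| Tmax (h) | ka (1/h) | Peak/trough, bd | Peak/trough, tds | 5 mg bd peak ÷ 10 mg bd trough | 10 mg bd peak ÷ 10 mg tds trough |
|---|---|---|---|---|---|
| 1.25 | 2.693 | 3.05 | 2.01 | 1.52 | 1.58 |
| 1.40 | 2.305 | 2.99 | 1.97 | 1.49 | 1.55 |
| 1.54 | 2.019 | 2.93 | 1.94 | 1.46 | 1.52 |
| 2.70 (fed) | 0.896 | 2.47 | 1.67 | 1.24 | 1.29 |

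The bd peak/trough ratio exceeds the 2-fold dose step in every row. A peak-time sample on the lower regimen would read above a trough on the higher one.

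**Step 3: if every sample were a trough.** With instantaneous input, the 8 h trough is proportional to 0.748 and the 12 h trough to 0.388, a ratio of 1.92. Daily dose rises from 20 to 30 mg, which is 1.5-fold. The part beyond daily dose is 1.92 / 1.5 = 1.28.

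**Step 4: spread within one dose level.** The diary accepts 2 h either way around an 8 h interval, so a trough could be taken 6 to 10 h after dose: 2^(4/6.53) = 1.53-fold. Section 4.4.1 gives 8 h as a minimum interval; the two texts need reconciling.

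**Step 5: AChE.** Assume inhibition decays as peak × 2^(−h/8.25), with no carry-over between doses.
- A 45% peak reads 45 × 2^(−8/8.25) ≈ 23% eight hours later, and so falls short of the 45% rule in SAP 8.3.
- A 30% peak reads about 18% at 6 h, 15% at 8 h and 11% at 12 h.
- Reading 45% at an 8 h trough would need a peak of about 88%.

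Whether a participant counts as reaching target can therefore depend on when the sample was drawn.

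**The case against.** Several stronger readings are tempting, and the documents do not support them.

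- **That the PK population would be empty.** SAP 4.5 gives plasma concentrations as an example of a steady-state PK parameter, and SAP 8.2 summarises them in their own right. One quantifiable sample can therefore qualify a participant under SAP 4.4. The set is empty only if parameter means a derived quantity such as Cmax. What remains is an ambiguity.
- **That time to target and duration cannot be obtained.** The protocol frames duration over the treatment period, so both are observable at visit resolution, in two-week steps. Hours per day above target are not observable, but the documents do not clearly ask for them. The missing piece is a definition.
- **That the plots would reflect sampling time.** Sample and in-clinic dose times are recorded, and a Week 8 draw is pre-dose. The plots could be confounded; it is not certain that they will be.
- **That the 1.9-fold rise in trough is all timing.** A true 1.5-fold rise in daily dose is inside it.
- **That one draw per visit is a stated fact.** It is inferred from Table 1, where a mark shows that a procedure happens, not how many tubes are drawn. An SOP could specify more. The pre-dose instruction in 9.18 also attaches to the Week 8 sample, not clearly to the whole series.

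It is also fair to say that SAP 8.2 carries a derivability proviso, that PK and AChE are other secondary endpoints handled descriptively, and that dose escalation rests on tolerability.

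Two things stand after all this. The unqualified promise in 9.18 of Cmax and half-life is not met by the schedule shown. The time of the last home dose, which a pre-dose sample needs, is not captured in the sample diary.

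**Conclusion.** The point holds in a limited form. On the schedule as written, individual Cmax, Tmax and half-life of phenserine cannot be derived. Time since dose is uncontrolled at Weeks 2 to 6 and only partly recoverable, so it could confound the exposure-response and AChE displays. Its possible size is a 2.5- to 3.1-fold peak/trough range on bd dosing against a 2-fold dose step, and a trough that rises about 1.28 times more than daily dose between 10 mg bd and tds.

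These sizes rest on linear one-compartment kinetics with evenly spaced doses, and on one draw per visit. Linearity is itself uncertain: Section 2.3.1 reports AUC rising only about 25% over a 4-fold dose increase. If exposure does rise less than in proportion to dose, the dose signal is smaller for a given timing effect. The AChE figures also assume exponential decay with the single half-life quoted in 4.5.

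The primary exosome comparison is not affected. This should be fixed, because the data are meant to inform Phase 2 dose selection and an unrecorded dose time is hard to reconstruct later.

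**What to change.** 1. Add one eCRF field per visit: date and time of the last dose before the PK and AChE samples. State in 9.18 and Table 1 the number of draws per visit and their timing relative to dose.
2. Unless an SOP already provides serial draws, replace Cmax and half-life in Protocol 9.18, and Cmax, Tmax and AUC in SAP 8.2, with phenserine concentration at a known time since dose. Show the exposure-response plots by time since dose, or adjust for it.
3. Define the PK population in SAP 4.4 as participants with at least one quantifiable concentration and a known dose time.
4. In SAP 8.3, report percent inhibition at each visit alongside time since dose. Define time to target as the first visit at or above 45% (two-week resolution), and duration as the number of visits at or above target.
5. Reconcile the donepezil PK text in Section 3 and Table 2 with 9.18 and 10.3, and clarify in 9.18 who is meant by all IMP participants and all other patients.

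The cost is protocol and SAP wording plus one eCRF field, with no new samples. The downside is fewer named PK parameters. For any visits already completed without a last-dose time, list the concentrations and mark time since dose as unknown.
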